### 6.3.4 Follow-up for toxicities

All patients will be followed for safety until 30 days after the last dose of INC280. Patients whose treatment is temporarily interrupted or permanently discontinued due to an AE or abnormal laboratory value must be followed until resolution or stabilization of the event, whichever comes first, including all study assessments appropriate to monitor the event.

An unscheduled assessment should be performed in all cases below where toxicity monitoring is recommended more frequently than defined by the schedule of assessments. Subsequent monitoring must be performed as per the regular visit schedule.

All patients should receive best supportive care (BSC) as per standard local practice for the treatment of pre-existing medical conditions or adverse events that may arise during the study. BSC is defined as drug or non-drug therapies, nutritional support, physical therapy, or any other treatment alternative that the investigator believes to be in the patient's best interest, but excluding other anti-neoplastic treatments (with the exception of radiotherapy for control of bone metastases – see [Section 6.4.1](#)).

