2.8.2 Safety

All safety analyses will be performed based on the Safety Set by cohort and also for all patients. Safety will also be presented combining the MET mutant cohorts and amplified cohorts as defined in [Section 2.2](#).

Baseline

Baseline is the result of an investigation describing the “true” uninfluenced state of the patient. The last available assessment before or on the start date of study drug is defined as “baseline” value or “baseline” assessment. If an assessment is planned to be performed prior to the first dose of study drug in the protocol and the assessment is performed on the same day as the first administration of study drug, it will be assumed that it was performed prior to study drug administration, if assessment time point is not collected or is missing. If assessment time points are collected, the observed time point will be used to determine pre-dose on study day 1 for baseline calculation. Unscheduled assessments will be used in the determination of baseline. See [Section 4.7.2](#) for further details on derivation of baseline for laboratory data and ECGs.

Patients who start treatment and discontinue from the study on the same day may have 2 different sets of data collected on study day 1, one being reported to the cycle 1 day 1 visit, the other reported to the end of treatment (EOT) visit. Data reported at the EOT visit are not eligible for baseline selection.

Grouping for the analyses

The overall observation period will be divided into three mutually exclusive segments:

- Pre-treatment period: from day of patient’s informed consent to the day before first dose of study drug
- On-treatment period:
 - For discontinued patients, from day of first dose of study drug to 30 days after last dose of study drug
 - For ongoing patients, from day of first dose of study drug to the data cut-off date
- Post-treatment period: starting at day 31 after last dose of study drug

The safety summary tables will include only assessments collected no later than 30 days after study drug discontinuation and assessments prior to the data cut-off date for on-going patients, unless otherwise specified.

For select items, shift tables or change from baseline summaries generated for laboratory, ECG, vital signs and change score generation may use data from pre-treatment period for baseline calculations.

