- Central nervous system toxicity
- Pancreatitis
- Photosensitivity
- Teratogenicity
- Drug-drug interactions with strong CYP3A4 inducers
- QTc interval prolongation

This classification reflects the current version of the eCRS and might be updated based on review of accumulating data.

For each specified AESI, number and percentage of patients with at least one event of the AESI occurring during on treatment period will be summarized.

Summaries of these AESIs will be provided by cohort, (specifying grade, SAE, relationship, leading to permanent treatment discontinuation, leading to dose adjustment/interruption, death, etc.).

Analysis of time to first occurrence of any grade AESI will be applied as well as time to first occurrence of grade 3/4 AESI using the Kaplan-Meier method (see below the definitions). Duration of first occurrence of grade 3/4 AESI will also be summarized. These analyses will be performed for AESI regardless of study drug relationship and for AESI suspected to be study drug related.

For time to first occurrence, failure curves (ascending Kaplan-Meier curves) will be constructed in the combined MET mutant cohorts and all patients. Median together with 95% CI as well as 25th and 75th percentiles will be presented. In addition, the median time to occurrence for the subset of patients who experienced the event of interest will be calculated. Simple descriptive statistics (median, min and max, 25th and 75th percentiles) will be presented. The probabilities at selected time points and the associate 95% CI will also be summarized.

Duration of first occurrence of grade 3/4 AESI will be presented for the subset of patients who experienced the event. Failure curves (ascending Kaplan-Meier curves) will be constructed in the combined MET mutant cohorts and all patients. Median together with 95% CI as well as 25th and 75th percentiles will be presented.

Duration of first occurrence of an event will be presented for the subset of patients of the safety set who experienced the event. A patient will be censored for time to resolution, if there is no resolution during the on-treatment period. The same censoring rules as described below for time to first occurrence apply.

Time to first occurrence

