- Time to first occurrence of an event is defined as time from start of study treatment to the date of first occurrence of this event (or first event within an AE grouping), i.e. time in days is calculated as (start date of first occurrence of event) – (start of study treatment) +1.
- In the absence of an event during the on-treatment period, the censoring date applied will be the earliest of the following dates: death date, new anti-neoplastic antineoplastic therapy start date, end date of on-treatment, analysis cut-off date, and withdrawal of informed consent date. See [Section 2.7.1](#) for the definition of new anti-neoplastic antineoplastic therapy.

Duration of first occurrence (i.e. Time to resolution of an event)

- Duration of first occurrence of an event is defined as time from onset to the date of resolution of the first event: (date of resolution of first event) – (date of onset of event) + 1.
- Resolution of the event means that outcome of the Grade 3/4 event is “recovered/resolved”, “recovered/resolved with sequelae”, or “recovering/resolving” (returning to grade ≤ 2). The same preferred term as the 1st event identified is used to determine the resolution. The resolution occurring after end of treatment + 30 days will be considered.
- The date of resolution of first Grade 3/4 event is derived as follows:
 - = End date of the first Grade 3/4 event *if the first event is resolved* (i.e. duration of AE). If multiple Grade 3/4 events with the same start date are reported, the latest end date will be considered (i.e. the longest duration of AE).
 - = Start date of the 1st Grade ≤ 2 event *if the first event is improved*. If multiple Grade 3/4 events with the same start date are reported, the latest start date of the

1st Grade \leq 2 event will be considered (i.e. the longest duration of first occurrence).

- = Start date of the 1st Grade \leq 2 event *if the first event is worsened and then improved*, and no Grade 3/4 AE with an outcome “resolved/recovered” reported later on. If multiple Grade 3/4 events with the same start date are reported, the latest start date of the 1st Grade \leq 2 event will be considered (i.e. the longest duration of first occurrence).
- = End date of the Grade 3/4 event reported with outcome “recovered/resolved” *if the first event is worsened and then resolved* and Grade 3/4 AE with an outcome “resolved/recovered” reported.

With

- *Worsened: Event with a non-missing end date and outcome “not recovered/ not resolved”*

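### SAP 2.8.2 gives two incompatible rules for the duration of the first grade 3/4 AESI when resolution falls more than 30 days after the last dose

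*SAP*

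**What the plan says.** All of the rules are in SAP section 2.8.2, in the text on AESIs.

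- **Definition.** "Duration of first occurrence of an event is defined as time from onset to the date of resolution of the first event", with one day added. Resolution includes improvement to grade 2 or lower.
- **Output.** "Duration of first occurrence of grade 3/4 AESI will be presented for the subset of patients who experienced the event", as Kaplan-Meier failure curves with the median and its 95% CI and the 25th and 75th percentiles.
- **First rule.** "A patient will be censored for time to resolution, if there is no resolution during the on-treatment period". The next sentence adds: "The same censoring rules as described below for time to first occurrence apply".
- **Imported censoring date.** For time to first occurrence, "the censoring date applied will be the earliest of the following dates": death, new antineoplastic therapy, end of the on-treatment period, analysis cut-off and consent withdrawal.
- **On-treatment period.** "For discontinued patients, from day of first dose of study drug to 30 days after last dose of study drug".
- **Second rule.** Under the heading that defines duration: "The resolution occurring after end of treatment + 30 days will be considered".

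SAP section 4.7.4 gives worked cases with event start and end dates but no last-dose dates. Protocol section 6.3.4 says that patients whose treatment is interrupted or stopped for an adverse event "must be followed until resolution or stabilization of the event, whichever comes first". Section 7.1.5.1 repeats this for permanent discontinuation. Neither sets a 30-day limit.

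**The concern.** Both rules concern the same endpoint and turn on the same day, last dose + 30. For a resolution after that day, the first gives a censored time and the second an event. Two programmers following the SAP faithfully could produce different tables for the final study report.

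Such records are plausible. Protocol Table 6-3 mandates permanent discontinuation for some events of this type, among them grade 3/4 ILD/pneumonitis and pancreatitis of grade 3 or above. Section 6.3.3 provides, with exceptions, for discontinuation after more than 21 consecutive days withheld. SAP section 2.6 takes the last non-zero dose as the last dose, so for a patient held and then stopped the 30 days start close to onset. Because follow-up runs to resolution or stabilization, later resolution dates can be in the database.

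At stake is how long these toxicities are reported to last, chiefly in the upper part of the distribution.

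**Working it through.** The plan states no figure to reproduce, so the check applies each rule to the same records.

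**1. SAP Case 4 (section 4.7.4).** Grade 3 hepatotoxicity, onset 17 Nov 2015, resolved with sequelae 19 Jan 2016.

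- Duration = resolution − onset + 1 = 63 + 1 = 64 days.
- If the last dose was *k* days after onset, the on-treatment period ends at onset + *k* + 30, so the censored time is *k* + 31.
- The two rules agree once *k* + 30 ≥ 63, that is *k* ≥ 33.

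The last-dose date is not given, so *k* is an assumption shown over its range:

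| Last dose, days after onset | First rule | Second rule |
|---|---|---|
| 0 | censored at 31 | event at 64 |
| 7 | censored at 38 | event at 64 |
| 16 | censored at 47 | event at 64 |
| 32 | censored at 63 | event at 64 |
| 33 or more | event at 64 | event at 64 |

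**2. The eight worked cases.** Their durations are 3, 51, 23, 14, 14, 24, 39 and 64 days (Cases 1a, 1b, 2a, 2b, 2c, 3a, 3b, 4). With onset on or before the last dose, resolution by day 31 is always inside the on-treatment period. Five cases then cannot differ; three (39, 51 and 64 days) can.

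**3. Second rule with the first rule's censoring date.** Suppose every patient stops drug on the onset day, so the boundary is day 31. Let *S* be the Kaplan-Meier proportion unresolved there, with *r* patients who resolve later and *u* who have no recorded resolution.

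- If the *u* patients are censored at the boundary, the later risk set is the *r* resolvers alone, and the curve falls to *S* × 0 = 0: everyone appears to resolve.
- If the *u* patients stay at risk while still assessed, it falls to *S* × *u*/(*u* + *r*). With *u* = *r* that is *S*/2.

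The gap is bias: whether a patient stays in the risk set depends on the later outcome.

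**4. Which statistics move (assumed inputs).** Simulation of 20 patients with an event, exponential time to resolution, and 25–75% stopping drug at onset (boundary day 31). The others have a boundary at day 400.

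| True median (days) | Runs where the KM median differs | Runs where the 75th percentile differs |
|---|---|---|
| 14 | none | 8–19% |
| 30 | 13–28% | 49–81% |
| 60 | 53–78% (typically 60–62 vs 57 days) | 67–86% |

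Nearly all simulated events resolve by day 400, so this shows sensitivity to the event rule, not the bias in step 3.

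**The case against.** The strongest reply is that the second sentence is a specific exception to a general rule: a late resolution is an event, and anything else is censored. It would hardly be needed otherwise. That is a possible reading, but so is a dropped *not*, and the text favours neither. Nor does the exception cure the problem, because the imported censoring date for unresolved patients still stands and produces the bias in step 3.

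Other objections stand and limit the point:

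- **Frequency.** A reader might infer that grade 3/4 AESIs usually end treatment. Table 6-3 does not support that: grade 3 AST/ALT, creatinine, asymptomatic amylase/lipase and QTc events allow dosing to resume. The on-treatment period then continues and the two rules often agree.
- **Not estimable.** A reader might infer that the first rule leaves the median unestimable. That needs nearly all patients to stop at onset. With an assumed exponential median of 40 days, the share unresolved at day 31 is 0.5^(31/40) = 0.58. If all 20 patients stop at onset, the chance of fewer than the 10 resolutions needed is about 71% (binomial, 20 patients, resolution probability 0.42). With 25–75% stopping at onset it is about 2% or less.
- **Reversibility.** The SAP does not list reversibility of serious toxicity as an output. The output is duration of the first grade 3/4 AESI, and Protocol section 8.1.2.1 says that grade 3 or 4 is not automatically serious.
- **Listings.** The SAP lists all data regardless of observation period, so late resolution dates would not be hidden.

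**Conclusion.** The conflict is real and is not settled elsewhere in the documents. It affects only first grade 3/4 AESIs that resolve after last dose + 30 days. Their number is not given; with none, the two rules count the same events. Where there are some, the upper quartile and confidence interval are the most exposed, and the median moves when typical durations approach or exceed about a month. The frequencies in the working rest on assumed durations, stopping proportions and sample size, and do not predict this trial's results.

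This is a minor point about a descriptive safety table. It does not touch ORR, any other efficacy endpoint or any hypothesis test. It merits correction because the text yields two answers and neither sentence can simply be laid over the other.

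**What to change.** In SAP section 2.8.2, use one event rule for duration and a censoring date that matches it:

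1. Count resolution whenever recorded, up to the analysis cut-off.
2. Censor unresolved events at the last date on which the event's status was assessed, and no later than death, consent withdrawal or cut-off. Do not use the last contact date of SAP section 4.3. It draws on survival follow-up and further-therapy dates, when the event may not have been under assessment, and would lengthen durations artificially.
3. State whether new antineoplastic therapy censors duration.
4. Remove the on-treatment censoring sentence for duration; keep the on-treatment rule for time to first occurrence.
5. Add last-dose dates to the worked cases in section 4.7.4, including one late resolution.

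The cost is a wording change and a small programming change, with no new data collection. One limit remains: follow-up may end at stabilization, so some events will have no resolution date and will be censored under any rule.

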4.7.4 Time to first occurrence of event and duration

This section provides additional details to those included in [Section 2.8.2](#). For each case, the start date and end date for the duration of the 1st occurrence are in bold.

Case 1a: First event resolved with a single event - Outcome = recovered/resolved

Patient ID	Preferred term	Start date	End date	Grade	Outcome
0001	INCREASED LIPASE	2016-05-31	2016-06-02	3	RECOVERED/RESOLVED

Case 1b: First event resolved with multiple events with the same start date - Outcome = recovered/ resolved

Patient ID	Preferred term	Start date	End date	Grade	Outcome
0002	INCREASED AMYLASE	2018-10-01	2018-10-29	3	RECOVERED/RESOLVED
	INCREASED LIPASE	2018-10-01	2018-11-20	3	RECOVERED/RESOLVED

Case 2a: The first event improved with a single event - Outcome = recovering/resolving

Patient ID	Preferred term	Start date	End date	Grade	Outcome
0003	ILD	2017-08-30	2017-09-20	3	RECOVERING/RESOLVING
	ILD	2017-09-21	2017-10-06	2	NOT RECOVERED/NOT RESOLVED
	ILD	2017-10-07		3	NOT RECOVERED/NOT RESOLVED

Case 2b: The first event improved with multiple events with the same start date - Outcome =recovering/resolving

Patient ID	Preferred term	Start date	End date	Grade	Outcome
0004	AST INCREASED	2017-11-30	2017-12-06	3	RECOVERING/RESOLVING
	HYPOALBUMINEMIA	2017-11-30	2017-12-06	2	RECOVERING/RESOLVING
	ALT INCREASED	2017-11-30	2017-12-13	3	RECOVERING/RESOLVING
	GGT INCREASED	2017-11-30	2018-01-12	2	RECOVERED/RESOLVED
	ALP INCREASED	2017-12-06	2017-12-13	1	RECOVERED/RESOLVED
	AST INCREASED	2017-12-06	2017-12-13	2	RECOVERING/RESOLVING
	ALT INCREASED	2017-12-13	2017-12-20	2	RECOVERING/RESOLVING
	AST INCREASED	2017-12-13	2017-12-20	1	RECOVERED/RESOLVED
	ALT INCREASED	2017-12-20	2018-01-12	1	NOT RECOVERED/NOT RESOLVED
	AST INCREASED	2018-01-12	2018-01-22	3	RECOVERING/RESOLVING
	ALT INCREASED	2018-01-12	2018-01-25	4	RECOVERING/RESOLVING

Case 2c: The first event improved (Gr 4, Gr 3 and Gr <3) - Outcome =recovering/resolving

Patient ID	Preferred term	Start date	End date	Grade	Outcome
0005	HEPATIC DYSFUNCTION	2017-01-06	2017-01-11	4	RECOVERING/RESOLVING
	HEPATIC DYSFUNCTION	2017-01-12	2017-01-18	3	RECOVERING/RESOLVING
	HEPATIC DYSFUNCTION	2017-01-19	2017-02-06	1	RECOVERED/RESOLVED

Case 3a: The first event worsened and then improved (Gr 3, Gr 4 and Gr <3) - Outcome =not recovered/not resolved and then recovering/resolving

Patient ID	Preferred term	Start date	End date	Grade	Outcome

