0006	AMYLASE INCREASE	2017-07-13	2017-07-18	2	RECOVERING/RESOLVING
	AMYLASE INCREASE	2017-07-19	2017-08-29	1	NOT RECOVERED/NOT RESOLVED
	AMYLASE INCREASE	2017-08-30	2017-09-05	3	NOT RECOVERED/NOT RESOLVED
	AMYLASE INCREASE	2017-09-06	2017-09-10	4	RECOVERING/RESOLVING
	AMYLASE INCREASE	2017-09-11	2017-09-21	3	RECOVERING/RESOLVING
	AMYLASE INCREASE	2017-09-22		1	NOT RECOVERED/NOT RESOLVED

Case 3b: The first event worsened with multiple events and then improved (Gr 3, Gr 4 and Gr <3) - Outcome =not recovered/not resolved and then recovering/resolving

Patient ID	Preferred term	Start date	End date	Grade	Outcome
0007	AMYLASE INCREASED	2017-09-12	2017-10-05	3	NOT RECOVERED/NOT RESOLVED
	AMYLASE INCREASED	2017-10-06	2017-10-20	3	RECOVERING/RESOLVING
	LIPASE INCREASED	2017-10-06	2017-10-20	1	RECOVERED/RESOLVED
	AMYLASE INCREASED	2017-10-20	2017-10-26	1	NOT RECOVERED/NOT RESOLVED
	LIPASE INCREASED	2017-10-26	2017-11-03	3	RECOVERED/RESOLVED
	AMYLASE INCREASED	2017-10-27	2017-11-20	3	RECOVERING/RESOLVING
	AMYLASE INCREASED	2017-11-20	2017-12-11	2	RECOVERED/RESOLVED
	AMYLASE INCREASED	2017-12-11		1	NOT RECOVERED/NOT RESOLVED

Case 4: The first event worsened and then resolved - Outcome =not recovered/not resolved and then recovered/resolved

Patient ID	Preferred term	Start date	End date	Grade	Outcome
0008	HEPATOTOXICITY	2015-11-17	2015-11-22	3	NOT RECOVERED/NOT RESOLVED
	HEPATOTOXICITY	2015-11-23	2015-12-02	4	RECOVERING/RESOLVING

	HEPATOXICITY	2015-12-03	2016-01-19	3	RECOVERED/RESOLVED WITH SEQUELAE
	GGT INCREASED	2016-01-05		2	NOT RECOVERED/NOT RESOLVED

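### SAP 2.8.2: for a first grade 3/4 AESI that worsened and then improved, a later resolved grade 3/4 recurrence of the same preferred term displaces the end date of the first occurrence (low priority)

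*SAP*

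**What the plan says.** In SAP 2.8.2, under the duration of first occurrence, the plan states: "Duration of first occurrence of an event is defined as time from onset to the date of resolution of the first event". The count is inclusive (difference in days plus 1). An outcome of recovering/resolving counts as resolution and is glossed as "returning to grade ≤ 2". On which records to use, the section says: "The same preferred term as the 1st event identified is used to determine the resolution".

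Four rules then give the resolution date. I number them in the order listed:

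1. First event resolved: its own end date.
2. First event improved: start of the first grade 2-or-lower record.
3. First event worsened and then improved: start of the first grade 2-or-lower record, "and no Grade 3/4 AE with an outcome “resolved/recovered” reported later on".
4. First event worsened and then resolved: "End date of the Grade 3/4 event reported with outcome “recovered/resolved".

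Whether a first event worsened is decided by how its record was closed: "Worsened: Event with a non-missing end date and outcome “not recovered/ not resolved". SAP 4.7.4 illustrates the rules with worked patients, including "Case 2a: The first event improved with a single event - Outcome = recovering/resolving" and "Case 3b: The first event worsened with multiple events and then improved".

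**The concern.** Neither rule 3 nor rule 4 says when the later resolved grade 3/4 record must occur. It need not precede the first return to grade 2 or below, and it need not belong to the same episode. A patient can therefore meet the SAP's own definition of resolution, have a separate grade 3/4 episode of the same term weeks later, and have the first occurrence extended to the end of the second. Rule 2 has no such condition, so the treatment of a recurrence turns on whether the first record was closed as not recovered or as recovering, and on the outcome code of the recurrence. Neither code measures how long the first event lasted.

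The output at stake is the Kaplan-Meier summary of duration of first grade 3/4 AESI (curves, median with 95% CI, quartiles). Sequences of several records are to be expected, because Protocol 8.1.1 asks for a new entry whenever an event worsens and whenever a grade 3 or 4 event improves.

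**Working it through.** The SAP prints no durations in days, and the bold type that marks the intended start and end dates in 4.7.4 is lost in the available text, so there is no printed figure to reproduce. The check applies the four rules literally, on the same preferred term, to the worked patients.

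Formula: duration = resolution date − onset date + 1.

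**Worked cases as printed**

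| Case | Course (same term) | Rule | Onset | Resolution | Days |
|---|---|---|---|---|---|
| 2a (0003, ILD) | grade 3, 2, 3 | 2 | 2017-08-30 | 2017-09-21 | 23 |
| 3a (0006, amylase) | grade 3, 4, 3, 1 from onset | 3 | 2017-08-30 | 2017-09-22 | 24 |
| 3b (0007, amylase) | grade 3, 3, 1, 3, 2, 1 | 3 | 2017-09-12 | 2017-10-20 | 39 |
| 4 (0008, hepatotoxicity) | grade 3, 4, 3 resolved | 4 | 2015-11-17 | 2016-01-19 | 64 |

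Each case falls under the rule that its heading names. (In Case 4, I read the variant spelling in the last hepatotoxicity row as the same term.)

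**Hypothetical change to Case 3b.** The amylase recurrence is grade 3 from 2017-10-27 to 2017-11-20, printed as recovering/resolving. Change only that outcome to recovered/resolved. The condition in rule 3 now fails, and rule 4 gives 2017-11-20:

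- 2017-11-20 − 2017-09-12 + 1 = 70 days, against 39.
- Difference 70 − 39 = 31 days; ratio 70/39 = 1.79.
- The 31 days are 6 further days at grade 1 (21 to 26 October; 20 October is already in the 39) plus the 25-day recurrence: 6 + 25 = 31.

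**Same course, first episode coded differently.** If the first episode is instead one record closed as recovering/resolving, rule 2 applies and the result is 39 days again, even with the recurrence closed as recovered/resolved. The 31 days therefore depend on outcome codes alone.

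**Narrow reading.** Suppose rule 4 is taken to exclude a patient who has already returned to grade 2 or below. Rule 3 still excludes that patient, because a later resolved grade 3/4 record exists. No rule then gives a date, although the definition of resolution has been met.

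**The case against.** The best defence is that the rules have to be read in context. Every rule is there to date the resolution of the first event, and the condition in rule 3 was probably written to separate Case 3a (grade 3, 4, 3, then 1) from Case 4 (grade 3, 4, 3, then resolved), both of which pass through a recovering record. Case 3a itself needs a contextual reading: patient 0006 has grade 2 and grade 1 amylase records from 2017-07-13 and 2017-07-19, before the grade 3 onset, and these plainly cannot be the return to grade 2 or below. On this view a later record should likewise mean one within the same episode. That is a fair account of intent, but the text does not state it, and the narrow reading leaves the patient without a date.

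Other parts of the defence stand and limit the point:

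- A reader might infer that any later resolved grade 3/4 event extends the duration. It does not: the same-preferred-term sentence rules that out. In patient 0007 the grade 3 lipase record resolved on 2017-11-03 would give 53 days if it counted, but it does not count.
- A reader might take Case 2a as proof that the SAP handles the same recurrence in two ways. Its later grade 3 ILD record is still open and not recovered, so it would not have triggered the rule 3 condition either. The difference lies in the rule text, not in a worked case.
- The trigger needs three things in one patient: a first grade 3/4 record closed as not recovered, a return to grade 2 or below, and a grade 3/4 recurrence of the same term closed as recovered/resolved.

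**Conclusion.** The point holds as a defect of wording with a narrow trigger. For the sequence described, the rules either date the first occurrence by the end of a separate recurrence or give no date, and both outcomes conflict with the SAP's definition of resolution.

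The move from 39 to 70 days shows how the rule behaves. A reader might take the 79% increase as an error already present in the SAP, but it appears only after a recorded outcome is changed; no printed case triggers it. Nor is the extension unlimited in practice: the rule sets no bound, but SAP 4.1 admits only data up to the cut-off. The documents do not allow the number of affected patients to be estimated.

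Only the descriptive summary of duration of first grade 3/4 AESI is affected. Adverse event incidence, grade tables, time to first occurrence and the efficacy endpoints are not, and no test or decision rests on the result. Low priority.

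**What to change.** In SAP 2.8.2, replace rules 3 and 4 with one rule. For a first grade 3/4 event that worsened, the resolution date is the earlier of:

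- (a) the start of the first grade 2-or-lower record of the same preferred term that starts after the onset of the first grade 3/4 event; and
- (b) the end date of the first grade 3/4 record of that term, at or after that onset, with outcome recovered/resolved, with or without sequelae.

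The words on onset are needed. Without them, (a) would pick the 2017-07-13 record for patient 0006 and give 2017-07-13 − 2017-08-30 + 1 = −47 days.

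Under this rule Case 3a stays at 24 days (only (a) applies), Case 3b at 39 (only (a)) and Case 4 at 64 (only (b)). Case 3b with the recurrence recoded as recovered/resolved also gives 39. Case 2a, under rule 2, stays at 23. Adding the recoded Case 3b to SAP 4.7.4 as a further example would settle the intent.

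The cost is a short SAP edit and a small change to the derivation program. No new data are needed.
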